10. MEASUREMENT OF EFFECT

Response is not the primary endpoint of the phase I component of this trial. However, participants with measurable disease will be assessed by RECIST and those who do not have measurable cancer via clinical response benefit (modified GCIg CA-125 response or stable disease for at least 16 weeks). For the purposes of this study, participants should be reevaluated for disease response based upon how their disease is being assessed. If RECIST criteria apply, patients should undergo a repeat radiographic assessment every 8 weeks (+/- 1 week) with CT or MRI scans. For patients with only elevated CA125 values, modified GCIg CA125 response will be measured every 4 weeks (+/- 1 week). In addition to a baseline scan, confirmatory scans should also be obtained at least 4 weeks following initial documentation of objective response. The next planned restaging CT Scan or MRI may be used as the confirmatory scan.

10.1. Measurable Disease Response Definition

When measurable lesions are present, response and progression will be evaluated in this study using the new international criteria proposed by the revised Response Evaluation Criteria in Solid Tumors (RECIST) guideline (version 1.1) [*Eur J Ca* 45:228-247, 2009]. Changes in only the largest diameter (unidimensional measurement) of the tumor lesions are used in the RECIST criteria.

10.1.1. Definitions

Evaluable for toxicity. All participants who receive at least one dose of study treatment will be evaluable for toxicity from the time of their first treatment with cediranib and olaparib.

Evaluable for objective response. Only those participants who have measurable disease present at baseline, have received at least one cycle of therapy, and have had their disease re-evaluated will be considered evaluable for response. These participants will have their response classified according to the definitions stated below. (Note: Participants who exhibit objective disease progression or die prior to the end of cycle 1 will also be considered evaluable.)

10.1.2. Disease Parameters

Measurable disease. Measurable disease are defined as those that can be accurately measured in at least one dimension (longest diameter to be recorded) as ≥ 20 mm by chest x-ray, as ≥ 10 mm with CT scan, or ≥ 10 mm with calipers by clinical exam. Measurable lesions must be at least 2 times the slice thickness in mm. All tumor measurements must be recorded in millimeters (or decimal fractions of centimeters).

Malignant lymph nodes. To be considered pathologically enlarged and measurable, a lymph node must be >15 mm when assessed by CT scan (CT scan slice thickness recommended to be no greater than 5 mm). At baseline and in follow-up, only the short axis will be measured and followed.

Non-measurable disease. All other lesions (or sites of disease), including small lesions (longest diameter <10 mm or pathological lymph nodes with ≥ 10 to <15mm short axis), are considered non-measurable disease. Bone lesions, leptomeningeal disease, ascites, pleural/pericardial effusions, lymphangitis cutis/pulmonis, inflammatory breast disease, abdominal masses (not followed by CT or MRI), and cystic lesions are all considered non-measurable.

Note: Cystic lesions that meet the criteria for radiographically defined simple cysts should not be considered as malignant lesions (neither measurable nor non-measurable) since they are, by definition, simple cysts.

‘Cystic lesions’ thought to represent cystic metastases can be considered as measurable lesions, if they meet the definition of measurability described above. However, if non-cystic lesions are present in the same patient, these are preferred for selection as target lesions.

Target lesions. All measurable lesions up to a maximum of 2 lesions per organ and 5 lesions in total, representative of all involved organs, should be identified as **target lesions** and recorded and measured at baseline. Target lesions should be selected on the basis of their size (lesions with the longest diameter), be representative of all involved organs, but in addition should be those that lend themselves to reproducible repeated measurements. It may be the case that, on occasion, the largest lesion does not lend itself to reproducible measurement, in which circumstance the next largest lesion which can be measured reproducibly should be selected. A sum of the diameters (longest for non-nodal lesions, short axis for nodal lesions) for all target lesions will be calculated and reported as the baseline sum diameters. If the lymph nodes are to be included in the sum, then only the short axis is added into the sum. The baseline sum parameters will be used as reference to further characterize any objective tumor regression in the measurable dimension of the disease.

Non-target lesions. All other lesions (or sites of disease) including any measurable lesions over and above the 5 target lesions should be identified as **non-target lesions** and should also be recorded at baseline. Measurements of these lesions are not required, but the presence or absence of each should be noted at each follow-up.

10.1.3. Methods for Evaluation of Measurable Disease

All measurements should be taken and recorded in metric notation using a ruler, calipers, or digital measurement tool. All baseline evaluations should be performed as closely as possible to the beginning of treatment and never more than 4 weeks before the beginning of the treatment.

The same method of assessment and the same technique should be used to characterize each identified and reported lesion at baseline and during follow-up. Imaging-based evaluation is preferred to evaluation by clinical examination when both methods have been used to assess the anti-tumor effect of a treatment.

Clinical lesions. Clinical lesions will only be considered measurable when they are superficial (e.g., skin nodules and palpable lymph nodes) and ≥ 10 mm diameter as assessed using calipers

(e.g., skin nodules). For the case of skin lesions, documentation by color photography, including a ruler to estimate the size of the lesion, is recommended.

Chest x-ray. Lesions on chest x-ray are acceptable as measurable lesions when they are clearly defined and surrounded by aerated lung; however, CT is preferable.

Conventional CT and MRI. This guideline has defined measurability of lesions on CT scan based on the assumption that CT slice thickness is 5mm or less. If CT scans have slice thickness greater than 5mm, the minimum size for a measurable lesion should be twice the slice thickness. MRI is also acceptable in certain situations (e.g. for body scans).

Ultrasound Ultrasound is not useful in assessment of lesion size and should not be used as a method of measurement. Ultrasound examinations cannot be reproduced in their entirety for independent review at a later date and, because they are operator dependent, it cannot be guaranteed that the same technique and measurements will be taken from one assessment to the next. If new lesions are identified by ultrasound in the course of the study, confirmation by CT or MRI is advised. If there is concern about radiation exposure at CT, MRI may be used instead of CT in selected instances.

Endoscopy, Laparoscopy. The utilization of these techniques for objective tumor evaluation is not advised. However, such techniques may be useful to confirm complete pathologic response when biopsies are obtained or to determine relapse in trials where recurrence following complete response (CR) or surgical resection is an endpoint.

Tumor markers. Tumor markers alone will not be used to assess response for the phase II portion of this study. If markers are initially above the upper normal limit, they must normalize for a subject to be considered in complete clinical response. Specific guidelines for both CA-125 response (in recurrent ovarian cancer) and PSA response (in recurrent prostate cancer) have been published [JNCI 96:487-488, 2004; *J Clin Oncol* 17, 3461-3467, 1999; *J Clin Oncol* 26:1148-1159, 2008]. In addition, the Gynecologic Cancer Intergroup has developed CA-125 progression criteria which are to be integrated with objective tumor assessment for use in first-line trials in ovarian cancer [JNCI 92; 1534-1535, 2000]. CA-125 response criteria and progression criteria are detailed further in Section 10.2.

Cytology, Histology. These techniques can be used to differentiate between partial responses (PR) and complete responses (CR) in rare cases (e.g., residual lesions in tumor types, such as germ cell tumors, where known residual benign tumors can remain). The cytological confirmation of the neoplastic origin of any effusion that appears or worsens during treatment when the measurable tumor has met criteria for response or stable disease is mandatory to differentiate between response or stable disease (an effusion may be a side effect of the treatment) and progressive disease.

10.1.4. Response Criteria

Evaluation of Target Lesions

Complete Response (CR): Disappearance of all target lesions. Any pathological lymph nodes (whether target or non-target) must have reduction in short axis to <10 mm.

Partial Response (PR): At least a 30% decrease in the sum of the diameters of target lesions, taking as reference the baseline sum diameters.

Progressive Disease (PD): At least a 20% increase in the sum of the diameters of target lesions, taking as reference the smallest sum on study (this includes the baseline sum if that is the smallest on study). In addition to the relative increase of 20%, the sum must also demonstrate an absolute increase of at least 5mm. (Note: the appearance of one or more new lesions (new lesions must be > slice thickness).

Stable Disease (SD): Neither sufficient shrinkage to qualify for PR nor sufficient increase to qualify for PD, taking as reference the smallest sum diameters while on study.

Unknown (UN): Assessment of target lesions cannot be made due to insufficient or unevaluable data. In this case, a concise explanation must be given.

Note: If tumor response data is missing, an overall assessment cannot be done. However, if there is missing or unevaluable data for non-target lesions, but data is available for all target lesions, the overall response for that time point will be assigned based on the sum diameters of all target lesions. Additionally, the assessment of CR cannot be made if there is missing or unevaluable data for non-target lesions. In this case, the overall assessment would be PR.

Evaluation of Non-Target Lesions

Complete Response (CR): Disappearance of all non-target lesions and normalization of tumor marker level.

Note: If tumor markers are initially above the upper normal limit, they must normalize for a subject to be considered in complete clinical response

Non-CR/Non-PD: Persistence of one or more non-target lesions and/or maintenance of tumor marker level above the normal limits.

Progressive Disease (PD): Appearance of one or more new lesions (new lesions must be > slice thickness) and/or unequivocal progression of existing non-target lesions.

Unknown (UN): Assessment of target lesions cannot be made due to insufficient or unevaluable data. In this case, a concise explanation must be given.

Note: Although a clear progression of "non-target" lesions only is exceptional, the opinion of the treating physician should prevail in such circumstances, and the progression status should be confirmed at a later time by review of the Principal Investigator (or Protocol Chair). Additionally, the cytological confirmation of the neoplastic origin of any effusion that appears or worsens during treatment is mandatory to differentiate between stable or progressive disease status.

Evaluation of Best Overall Response

The best overall response is the best response recorded from the start of the treatment until disease progression/recurrence (taking as reference for progressive disease the smallest measurements recorded since the treatment started). The participant's best response assignment will depend on the achievement of both measurement and confirmation criteria.

Target Lesions	Non-Target Lesions	New Lesions	Overall Response	Best Response for this Category Also Requires:
CR	CR	No	CR	≥ 4 wks confirmation
CR	NonCR/Non-PD	No	PR	≥ 4 wks confirmation
CR	Not evaluated	No	PR	
PR	Non-PD/not evaluated	No	PR	
SD	Non-PD/not evaluated	No	SD	Documented at least once ≥ 4 wks from baseline**
PD	Any	Yes or No	PD	No prior SD, PR or CR
Any	PD*	Yes or No	PD	
Any	Any	Yes	PD	
* In exceptional circumstances, unequivocal progression in non-target lesions may be accepted as disease progression. ** Only for non-randomized trials with response as primary endpoint Note: Participants with a global deterioration of health status requiring discontinuation of treatment without objective evidence of disease progression at that time should be reported as "symptomatic deterioration". Every effort should be made to document the objective progression even after discontinuation of treatment.				

10.2. CA-125 Response Definition

For patients enrolled in this study with no measurable cancer but elevated CA125 levels, these subjects enrolled will have CA-125 levels at least twice the upper limit of normal (see Section 3.1.2). The GCIG CA-125 response criteria (Rustin, 2003), which are a better prognostic tool than RECIST in second-line cytotoxic therapy of ovarian cancer (Gronlund *et al.*, 2004), will be

modified to assess CA-125 response to combination therapy with cediranib and olaparib. The original criteria were developed for the use of cytotoxic agents, which generally produce a rapid decline in CA-125 levels in patients with chemosensitive disease. However, combination therapy with an anti-angiogenic and a PARP-inhibitor may produce either disease stability, due to its cytostatic nature, or disease response of a more gradual tempo, based on mechanism of action. Thus, it may take more time for CA-125 responses (and tumor measurement responses) to be seen with cediranib/olaparib combination therapy. Towards that end, we have modified the timing of response determination set out by the GCIG.

10.2.1. Baseline CA-125 Level for Response Assessment

Two pretreatment CA-125 samples must be at least twice the upper limit of normal (at least 1 day but not more than 3 months apart; at least one of the samples should be within 1 week of starting treatment). **A CA-125 level drawn just prior to (within 1 week of) Cycle 1 Day 1 will be used as the BASELINE CA-125.**

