3.1. Inclusion Criteria

Potentially eligible patients will be screened by their gynecologic oncologist and/or medical oncologist. Participants must meet the following criteria on screening examination to be eligible to participate in the study:

- 3.1.1. For Phase I Portion:** Participants must have histologically or cytologically confirmed epithelial ovarian cancer, primary peritoneal serous cancer, fallopian tube cancer, or triple-negative breast cancer.

For Phase II Portion: Participants must have histologically or cytologically Grade 2 or 3 (high-grade) papillary-serous or endometrioid epithelial ovarian cancer, primary peritoneal serous cancer, or fallopian tube cancer. Participants with epithelial ovarian, primary peritoneal, or fallopian tube cancers of other high-grade histologies who carry a known deleterious BRCA germline mutation by standard clinical testing (Myriad BRCAAnalysis) will also be considered eligible.

For Phase I-T Portion: Participants must have histologically or cytologically confirmed epithelial ovarian cancer, primary peritoneal serous cancer, or fallopian tube cancer.

- 3.1.2.** Ovarian cancer, primary peritoneal, and fallopian tube participants in the Phase 1 and Phase 1-T portions of this trial must have either measurable cancer by RECIST 1.1 criteria or an elevated CA125 level at least twice the upper limit of normal on two separate occasions at least 1 day but not more than 3 months apart. At least one of the samples should be within 1 week of starting treatment. Patients with both an elevated CA125 and measurable cancer will be followed by RECIST 1.1 criteria. Patients with only an elevated CA125 level will be followed by modified GCIG criteria, as detailed in Section 10.2.

Participants in the Phase II portion of the trial must have measurable disease by RECIST 1.1 criteria.

Breast cancer participants must have measurable disease by RECIST criteria.

- 3.1.3.** Prior therapy:

For Phase I and Phase I-T Portions:

- Prior chemotherapy for ovarian cancer patients must have included a first-line platinum-based regimen with or without intravenous consolidation chemotherapy.
- Breast cancer patients must have recurred post both an adriamycin- and taxane-containing regimen.
- Prior hormonal-based therapy for ovarian, primary peritoneal serous, fallopian tube cancer, or breast cancer is acceptable.

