Toxicity assessments will be done using NCI Common Terminology Criteria for Adverse Events (CTCAE v4.0). CTCAE v4.0 is identified and located on the CTEP website at (http://ctep.cancer.gov/protocolDevelopment/electronic_applications/ctc.htm). Dose escalation to the next dose level will occur when the preceding cohort reaches the end of Cycle 1. Patients who do not complete both treatments in cycle 1 for reasons other than cediranib or olaparib toxicity will be replaced. Toxicity data for each cohort will be reviewed prior to dose escalation. Intra-patient dose escalation will be allowed at the discretion of the investigator and overall trial PI for patients following their completion of Cycle 2 if the following criteria are met: the patient had no > grade 1 toxicities secondary to study treatment except for grade 2 or 3 HTN or nausea no greater than grade 1 after treatment with concurrent medications, the subsequent dose cohort has completed Cycle 1, and evaluation of DLTs has been completed for the subsequent dose cohort and the dose was deemed to be safe due to ≤ grade 2 toxicities. Dose escalation will occur for both cediranib and olaparib according to the dose escalation schema. Patients can be dose-escalated multiple times as long as they continue to meet criteria and do not exceed the final protocol-specified dose level (dose Level 3). All intra-patient dose escalations must be discussed and approved by the overall trial PI. If treatment-related toxicities related to one of the study drugs restricts further escalation of that drug, a modification to the dose escalation schema may be considered.

Phase I-T PK expansion

Once the MTD has been established during the Phase 1-T, two PK expansion cohorts of 6 evaluable patients each will be enrolled for pharmacokinetic studies. Participants in this expansion will receive a one week of either single-agent cediranib (Cohort 1-T PKced) or single-

agent olaparib (tablet formulation; Cohort 1-T PKolap) prior to starting cycle 1 of combination cediranib and olaparib (tablet formulation). Full details of the PK evaluation schedule are outlined in Section 8.14. Participants must be able to continue on study drug without any dose holds through Cycle 1 Day 16 of treatment to be considered fully evaluable for PK studies.

Participants participating in the PK expansion cohorts will take their study drugs on the following schedule once combination dosing has started:

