8.14. Pharmacokinetic (PK) studies

The steady-state plasma pharmacokinetics of cediranib and olaparib will be defined in a group of 12 patients in the safety expansion cohort treated with the recommended phase II doses of the combination, cediranib 30 mg QD and olaparib 200 mg BID, to assess whether or not the pharmacokinetic behavior of the two drugs is altered by their concurrent administration. Pharmacokinetic sampling will be performed during a single 24 h dosing interval after steady-state pharmacokinetic conditions for the repeated oral dosing schedules have been achieved when each agent is given alone (cycle 0) and again when given together in the same patient (cycle 1). In cycle 0, one group of six patients will receive single agent cediranib p.o. once daily for 7 days and the other group of six patients will receive single agent olaparib p.o. twice daily for 7 days. Pharmacokinetic samples will be collected on day 7 before and for 8 h after the dose is taken in the morning and before dosing on day 8. Combination therapy will begin on day 8 which is formally day 1 of cycle 1. Pharmacokinetic samples will again be collected before and for 8 hr after dosing on days 15-16 after the patients have received 14 days of combined therapy, as per the timepoints outlined below.

The sampling schedule has been devised to accommodate treatment on an outpatient basis. Patients will be instructed to take the doses of the two drugs as per outlined in the protocol at the same time every day during the pharmacokinetic study. Cediranib will be taken first thing in the morning on an empty stomach. One hour later, the patient may have a light meal, followed by the morning dose of olaparib. Dosing should be scheduled for times that will allow the patient to arrive at the clinic to obtain pharmacokinetic samples before dosing and to remain for an additional 8 hours after the morning dose of olaparib. The second daily dose of olaparib should be taken 12.0 ± 0.25 h after the morning dose. It is very important that the patient is aware that the morning doses of the two drugs on day 8 and day 16 must not be taken before arriving at the clinic and the 24.0 h pharmacokinetic sample has been collected. The first set of blood samples (6 mL) will be obtained during cycle 0 shortly before taking the day 7 dose of the single agent drug and at 0.5, 1.0, 2.0, 3.0, 4.0, 6.0, 8.0, and 24.0 h after dosing.

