- k: If patients have no measurable cancer for RECIST assessment, the patient must have two pretreatment CA-125 samples that are at least twice the upper limit of normal (at least 1 day but not more than 3 months apart; at least one of the samples should be within 1 week of starting treatment). A CA-125 level drawn just prior (within 1 week of) to Cycle 1 Day 1 of cediranib/olaparib dosing will be used as the BASELINE CA-125. CA-125 will be drawn at the start of each cycle.
- l: Tumor measurements by CT scans or MRI will be performed within the 4 weeks prior to starting cediranib/olaparib and will be performed after every 8 weeks (+/- 1 week) of treatment. If a partial or complete response is noted, a confirmatory CT scan or MRI should be performed. The next planned restaging CT scan or MRI may be used as the confirmatory scan.
- m: For patients in the Phase 1 portion of the trial who have been on trial for greater than 1 year without evidence of disease progression, the treating investigator may choose to decrease the frequency of re-staging CT scans to once every 4 cycles.
- o: For patients in the Phase 1 portion of the trial who have been on trial for greater than 3 years without evidence of disease progression, the treating investigator may choose to decrease the frequency of visits to once every 2 cycles. These patients should have CBC with differential, serum chemistry, and urine protein assessment (UPC or urinalysis) performed and con-meds, adverse events, and blood pressure diary should be reviewed in-person or by telephone with the study team, but all other assessments may be omitted.
- p: Reference section 8.14 of the protocol for further information on exact timing requirements of samples.

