10.2.2. Definition of CA-125 Response

CA-125 levels will be drawn at the start of each cycle. A CA-125 response occurs if, after two elevated levels before therapy, a subsequent sample (taken at least 4 weeks +/- 1 week after initiating cediranib/olaparib) shows at least a 50% decrease that is confirmed by a sequential confirmatory sample (taken 4 weeks +/- 1 week after the prior sample). The confirmatory sample must be less than or equal to 110% of the prior sample showing a response.

10.2.3. Definition of CA-125 progression:

No validated definitions of CA-125 progression have been published to date. Given the potential cytostatic nature of angiogenesis inhibitors such as cediranib, in this trial the criterion for progression based on CA-125 level is: **doubling of the CA-125 level from BASELINE (pre-treatment).**

As long as interval CA-125 measurements are less than double the value from baseline, subjects may continue on study, provided that tumor measurements are stable as well, without the development of new lesions.

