14.3. Reporting and Exclusions

14.3.1. Evaluation of Toxicity

All patients will be evaluable for toxicity from the time of their first treatment with cediranib and olaparib.

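### In the Phase I-T PK expansion, the CA-125 baseline rule favours a value taken after a week of single-agent drug, although the plan labels that baseline pre-treatment

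*Combined protocol and SAP*

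**What the plan says.** **Who is followed by CA-125.** Section 3.1.2 admits Phase I-T patients with or without measurable disease. Those with both measurable disease and a raised CA-125 are followed by RECIST. For the rest: "Patients with only an elevated CA125 level will be followed by modified GCIG criteria, as detailed in Section 10.2".

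**The run-in.** Section 5 plans that "two PK expansion cohorts of 6 evaluable patients each will be enrolled for pharmacokinetic studies". Section 8.14 describes it: "In cycle 0, one group of six patients will receive single agent cediranib p.o. once daily for 7 days". The other six take olaparib alone for the same period. Then: "Combination therapy will begin on day 8 which is formally day 1 of cycle 1".

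**The baseline.** Section 10.2.1 states: "A CA-125 level drawn just prior to (within 1 week of) Cycle 1 Day 1 will be used as the BASELINE CA-125". Footnote k of the Phase I and I-T calendar (Section 9.1) is more explicit that the anchor is combination dosing: "A CA-125 level drawn just prior (within 1 week of) to Cycle 1 Day 1 of cediranib/olaparib dosing". Neither place makes an exception for cycle 0, and the calendar has no cycle 0 column.

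**How the baseline is labelled and used.** Section 10.2.2 defines response as a confirmed fall of at least 50%. Section 10.2.3 defines progression as "doubling of the CA-125 level from BASELINE (pre-treatment" value. Section 10.4.2 also describes the reference for CA-125 progression as a pretreatment measurement. The introduction to Section 9 asks for assessments before any study drug is given.

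**The concern.** Section 10.2.1 uses two anchors in one paragraph. The qualifying sample is tied to the start of treatment, the baseline to Cycle 1 Day 1. In the escalation cohorts these are the same day. In the PK expansion they are a week apart, and the week between them is spent on active drug, with a different drug in each cohort.

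A draw at Cycle 1 Day 1 is to be expected in practice, because CA-125 is taken at the start of every cycle. Calendar footnote a excuses repeat laboratory work only if screening fell within 7 days of that date. A data manager who follows Section 10.2.1 and footnote k to the letter would normally enter that on-treatment value as baseline.

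Both CA-125 cut-offs are multiples of this one number. Clinical benefit and PFS are Phase I-T secondary objectives in Section 1.3.4, so an on-treatment reference would shift when response and progression are called for these patients. Section 10.2.3 also ties remaining on study to the same doubling. The passages therefore need to be reconciled for that use too.

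**Working it through.** **Inputs.** Run-in of 7 days, two groups of six (Sections 5 and 8.14). At least one qualifying CA-125 no more than a week before treatment starts (Sections 3.1.2 and 10.2.1). Baseline no more than a week before Cycle 1 Day 1 (Section 10.2.1; Section 9.1, footnote k). Response at 0.5 and progression at 2 times baseline (Sections 10.2.2 and 10.2.3). Start of treatment is taken to mean the first dose of either study drug.

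**Step 1: reproduce the plan's calendar.** 7 run-in days + 1 = dosing day 8 for Cycle 1 Day 1, as Section 8.14 states. Patients exposed: 2 x 6 = 12 evaluable.

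**Step 2: compare the two sampling windows.** Set Cycle 1 Day 1 as day 0, so the first run-in dose is on day -7.

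- Qualifying sample: days -14 to -7.
- Baseline sample: days -7 to 0, which is 8 calendar days.
- Overlap: day -7 only, and only if the draw precedes the first dose.
- Baseline-window days after the day of first dosing: -6 to 0, which is 7 of the 8.

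Without a run-in, the first dose is on day 0, both windows are days -7 to 0, and the conflict disappears.

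**Step 3: effect on the cut-offs.** Let c be the proportional change in CA-125 between the pre-run-in sample and the value used as baseline. Relative to the true pre-treatment level, response is called at 0.5 x (1 + c) and progression at 2 x (1 + c). The documents give no value for c; the range below is an assumption for illustration.

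| Assumed change c | Response cut-off (x true baseline) | Progression cut-off (x true baseline) |
|---|---|---|
| -30% | 0.35 | 1.40 |
| -20% | 0.40 | 1.60 |
| -10% | 0.45 | 1.80 |
| 0 | 0.50 | 2.00 |
| +10% | 0.55 | 2.20 |
| +20% | 0.60 | 2.40 |
| +30% | 0.65 | 2.60 |

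If CA-125 falls during the run-in, response becomes harder to reach and progression is called at a lower level. If it rises, the reverse holds.

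**The case against.** The strongest reply is that the text does not force an on-treatment baseline. A pre-dose draw on run-in day 1 is exactly one week before Cycle 1 Day 1 and satisfies every rule. The Section 9 introduction, the pre-treatment labels, and the requirement in Section 10.2.2 for two raised values before therapy all pull towards that sample. This stands, and it limits the point: the plan supports two different baselines, and the wording of Section 10.2.1 and footnote k favours the later one.

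The reach is also small. The cohorts exist for within-patient PK, no efficacy comparison of expansion with escalation patients is planned, and Section 14.1.5 lists only toxicity as a Phase I-T secondary endpoint. The number of CA-125-only patients among the 12 is not given and could be zero. All of this stands.

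Three stronger readings are tempting, and the documents do not support them.

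- **Toxicity start misplaced.** Section 14.3.1 says "All patients will be evaluable for toxicity from the time of their first treatment with cediranib and olaparib", from which a reader might infer that run-in events fall outside the evaluable period. But the matching sentence in Section 10.1.1 opens by making anyone with at least one dose of study treatment evaluable. Sections 6 and 11.1 collect adverse events from the first dose. The Phase II control arm takes olaparib only, so naming both drugs must be shorthand for study treatment.
- **PFS and stable disease started late.** Sections 10.4.3 to 10.4.5 already count both from the start of treatment, not from Cycle 1 Day 1.
- **A large, known CA-125 fall in one week.** No source in the documents gives a rate of change, and Section 10.2 expects responses of a gradual tempo.

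**Conclusion.** The point holds as a minor inconsistency. For CA-125-only patients in the PK expansion, the written baseline rule favours a value taken after up to 7 days of single-agent treatment, against the plan's own description of that value as pre-treatment.

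The size of the effect is unknown. It is proportional to the run-in change in CA-125, and the range of -30% to +30% is an illustration, not an estimate. At most 12 PK-evaluable patients are exposed, fewer once those with measurable disease are set aside. Only Phase I-T secondary efficacy is touched. The MTD is unaffected because the expansion opens after it has been established. Phase II is unaffected because it requires measurable disease and has no run-in.

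This conclusion rests on the literal wording of Section 10.2.1 and footnote k, and on reading the start of treatment as the first dose of either drug.

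**What to change.** In Section 10.2.1 and in footnote k of Section 9.1, define the baseline as the last CA-125 drawn before the first dose of any study drug, and add that in the PK expansion this means before dosing on cycle 0 day 1. That makes the rule agree with the pre-treatment label in Sections 10.2.3 and 10.4.2 and with the Section 9 introduction. Because Section 10.2.3 uses the same baseline for remaining on study, the investigators should confirm that the reconciled text is also what they intend there.

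The cost is wording only. CA-125-only patients must already have a sample no more than a week before treatment starts, so no extra draw or visit is needed.

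Optionally, Sections 10.1.1 and 14.3.1 could start toxicity evaluability at the first dose of study treatment, to match Sections 6 and 11.1. That is tidying, not a correction. The PFS and stable-disease definitions need no change on this account.
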